# 8.4 Statistical methods for the analysis of the exploratory efficacy endpoints: comparisons internal to the DCVax®-L study

#### 8.4.1 Immunostimulatory response

A subject will be considered a responder if one of the following conditions holds:

- T cell proliferative response to DCVax®-L shows a stimulation index of 2 or greater;
- A greater than 3-fold increase in CD8+ cells staining with tumor antigen tetramers.
- An ELISPOT response exceeding background signal by at least 2 standard deviations. The background signal will be based on the level of response in patients randomized to placebo

Immunostimulatory response will be analyzed as a binary outcome. Logistic regression will be used, with the following covariates:

- Sex: Male / female
- Age at randomization: years
- MGMT status at randomization: Yes, No, unknown
- Karnofsky Performance Status at randomization: score
- Extent of resection: Complete / partial (or incomplete)
- Absolute lymphocyte count at randomization:  $\leq 1,000 / \mu L$ ,  $> 1,000 / \mu L$ , unknown

#### 8.4.2 Physical functioning

Physical functioning will be measured by the Karnofsky performance status (KPS). Both the score and the change from baseline will be summarized, and the change from baseline will be compared between the treatment groups and the controls groups using the Wilcoxon test stratified by MGMT methylation status. This analysis will be conducted for each visit separately.

The time from date of surgical resection to a 10-point decline in KPS will calculated. This endpoint will be analyzed using the Karrison approach as for the analysis of the secondary endpoints within study PFS and OS.

#### 8.4.3 Time to progression (TTP)

Time to progression (TTP) is defined as the time from randomization to disease progression (per modified Macdonald criteria determined by independent ICON Medical Imaging review).

Progression is censored when a uuPD occurs. For patients who die before experiencing progression or uuPD, progression is censored at death. Within-Study controls are used for this endpoint.

TTP will be analyzed using a cause-specific Cox proportional hazards regression model [31].

#### 8.4.4 Tumor response

Tumor response will be defined in three ways:

- Complete response
- Complete or partial response
- Complete or partial response or stable disease.

Each will be analyzed as a binary outcome. Logistic regression will be used, with covariates as defined for the primary analysis of the primary endpoints.

#### 8.4.5 Ultimately unconfirmed progression

A KM plot of the percentage of subjects who had a progression event during the trial and who are free of uuPD events (as defined in Section 3.2.5) versus time by treatment arm is intended to aid in the interpretation of influence of vaccine-induced, pseudo-progression, if any, on the analysis of the primary and secondary endpoints. One example is that an increase incidence over time in the intervention group relative to the control group in uuPD could possibly be an indication of the presence of vaccine-induced, pseudo-progression in the analysis of OS, cPFS and PFS.

Overall survival will be compared between patients who had a progression event during the trial and then experience an uuPD and those that experience a cPD, regardless of treatment group.

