#### 1.2.3 Additional secondary endpoints: PFS and OS comparing arms within trial

After the Primary Endpoint and Secondary Endpoint #1 are analyzed in comparison with external controls, as described above, several additional Secondary Endpoints will be analyzed in a comparison between the two arms or cohorts within the Trial. These analyses are shown below.

Secondary Analysis: DCVax-L Statistically significant Endpoint #2: compared to separation of the curves **Confirmed PFS** placebo Analysis: DCVax-L **Evidence of** Secondary Statistically significant YES compared to Endpoint #3: PFS separation of the curves Benefit placebo Analysis: DCVax-L Secondary Statistically significant compared to Endpoint #4: OS separation of the curves

Figure 2: Additional Secondary Endpoints: Comparisons Within Trial

placebo

**Secondary Endpoint #2:** Confirmed Progression Free Survival (cPFS) - Comparison between subjects randomized to DCVax®-L and those randomized to Placebo within Study 020221.

As explained above, it has become well recognized that pseudo-progression (PsPD) may occur in a substantial percentage of patients (e.g., up to 30% of brain cancer patients). Traditional methods of analysing progression tend to rely upon one set of MRI scans at the time when progression or

pseudo-progression appears. It has been observed that pseudo-progression (e.g., edema) may subside over time while real progression will not. So, analysing a series of MRI scans and other measures in order to confirm progressive disease should help obtain a more accurate assessment of real vs. pseudo-progression.

For purposes of the Secondary Endpoint #2, Confirmed Progressive Disease (cPD) is defined as initial disease progression determined through independent review (unconfirmed PD), AND also either (i) a new lesion or (ii) any one of the following criteria (modified iRANO criteria):

- A further 25% increase or greater in the sum of bi-perpendicular diameters of enhancing tumor, occurring at least 4 weeks after the initial event of PD/PsPD;
- Significant increase in T2/FLAIR non-enhancing lesion attributable to tumor growth;
- Death (all deaths are counted as events).

A secondary analysis will, in addition to the MRI findings, take into account the clinical status of the patient, as follows:

- Non-temporary increase in steroid dose >2 mg/day not associated with the unconfirmed PD event:
- Significant clinical decline not attributable to other causes;

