#### 3.2.5 Ultimately unconfirmed progression

For the cPFS (confirmed PFS) endpoint, events that have been preliminarily identified as disease progression by MRI (uPD events) are classified as cPD events if subsequent scans or medical review demonstrate further progression. The remaining uPD events will be classified as uuPD events, for ultimately unconfirmed disease progression. These uuPD events will by default include events that are not reflective of actual disease progression and will therefore contain a large proportion of the pseudo-progression events, including those induced by DCVax®-L vaccination, that may have occurred in this study.

A KM plot of the percentage of subjects free of uuPD events versus time by treatment arm is intended to aid in the interpretation of the influence of vaccine-induced, pseudo-progression, if any, on the analysis of the primary and secondary endpoints. One example is that an increase incidence in uuPD events over time in the DCVax®-L treatment group relative to the control group could possibly be an indication of the presence of vaccine-induced, pseudo-progression in the analysis of OS, cPFS and PFS.

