## 15.2. DEFINITION OF PROGRESSION AFTER ENROLLMENT

Progression, calculated from the nadir tumor burden (i.e. post operative orBaseline), is defined as one of the following:

- In the case of complete resection during primary therapy: a new measurable tumor at
  the site of the resected tumor, defined as a mass with a longest diameter equal to or
  greater than 1 cm in at least one dimension. If progression is not defined by these
  studies, treatment may proceed and determinations made at the next scheduled MRI.
- In the case of incomplete resection during primary therapy: a 25% increase or greater
  in the residual tumor if the recurrent portion of the tumor is at least 1 cm or greater in
  its longest diameter, measured by MRI and confirmed by scans above as attributable
  to tumor growth;
- If resection is indicated for recurrent disease, while radiographic criteria for progression have not been met: surgical resection, subsequently confirmed as

progressive GBM by Pathology at the clinical site and to be confirmed by independent pathology;

- Appearance of any new lesion/site at least 1 cm in at least one dimension or greater measured by MRI and confirmed by scans above;
- Unequivocal progression of non-measurable disease (either non-enhancing disease seen only on T2/FLAIR images or enhancing disease not meeting size criteria for measurability), such that there is confidence that tumor growth has occurred;
- Death: all deaths are counted as events for the primary endpoint.

Radiographic evidence of disease progression will be evaluated and corroborated by independent radiology review to determine disease progression for purpose of this trial. MRIs to assess disease progression are done every 2 months. Unscheduled MRIs or other testing will be recorded in CRFs/eCRFs. If, during unscheduled procedures, there is evidence of disease progression, it must be confirmed through independent review as described above.

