#### 15.3. DEFINITION OF CONFIRMED PROGRESSION AFTER ENROLLMENT

For purposes of the new Secondary Endpoint #2, Confirmed Progressive Disease (cPD) will be defined as initial disease progression determined through independent review (a.k.a. unconfirmed PD), AND also either (i) a new lesion or (ii) any one of the following criteria (modified iRANO criteria):

- A further 25% increase or greater in the sum of bi-perpendicular diameters of enhancing tumor, occurring at least 4 weeks after the initial event of PD/PsPD;
- Significant increase in T2/FLAIR non-enhancing lesion attributable to tumor growth;
- Death (all deaths are counted as events).

A secondary analysis will, in addition to the MRI findings, take into account the clinical status of the patient, as follows:

- Non-temporary increase in steroid dose >2 mg/day not associated with the unconfirmed PD event;
- Significant clinical decline not attributable to other causes;

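### The exploratory survival comparison of unconfirmed with confirmed progression (SAP 8.4.5) sorts patients partly by how long they lived, so it is biased by construction

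*Combined protocol and SAP*

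**What the plan says.** SAP 8.4.5 plans a Kaplan-Meier plot of freedom from uuPD by arm and then adds one further analysis: "Overall survival will be compared between patients who had a progression event during the trial and then experience an uuPD" and those with cPD, regardless of arm. It names no time origin, test, model or significance level. It falls under the SAP 8.4 heading, "Statistical methods for the analysis of the exploratory efficacy endpoints", outside the alpha hierarchy.

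SAP 8.4.5 takes the meaning of uuPD from SAP 3.2.5. There, initial progression events (uPD) are "classified as cPD events if subsequent scans or medical review demonstrate further progression", and "The remaining uPD events will be classified as uuPD events, for ultimately unconfirmed disease progression". Death is not named.

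SAP 1.2.3 and protocol 15.3 also define cPD, for the same confirmed-PFS endpoint, with a list of confirming criteria. One is a further size increase "occurring at least 4 weeks after the initial event of PD/PsPD". Another reads "Death (all deaths are counted as events". Protocol 15.2 sets the imaging interval: "MRIs to assess disease progression are done every 2 months".

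**The concern.** A patient's group is not known at the first progression call. It is fixed by what follows, and one thing that can follow is death.

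- **Under 3.2.5,** early death leaves a patient unconfirmed, so uuPD collects early deaths. A patient confirmed on a later scan is guaranteed to have survived until that scan (immortal time). Both effects make uuPD look worse.
- **If death confirms,** every patient who dies after a first progression call is cPD, and uuPD holds only patients who were alive or censored. uuPD then looks immortal.

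SAP 3.2.5 expects uuPD to contain a large share of the pseudo-progression events, so readers will take a survival contrast between the groups as evidence on that expectation. Under the first rule it can produce false evidence against it; under the second, false support.

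**Working it through.** The plan gives no sample size, power or error rate for this comparison, so there is no figure to reproduce.

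**Inputs from the documents.** MRI every 2 months (protocol 15.2). Median post-progression survival 5.5 to 12.6 months (SAP Table 6 control arms), with 25.3 − 11 = 14.3 months as an upper case (SAP 1.3). Median PFS 7 or 11 months, 331 patients, loss 1% per month (SAP Introduction and 1.3). Pseudo-progression in "up to 30% of brain cancer patients" (SAP 1.2.3), used to set the share of events that can never be confirmed.

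**Assumed.** Exponential times, 5 to 13 years of follow-up, log-rank test, two-sided 5%, and the chance of confirmation per scan. Confirmability is drawn independently of survival, so the true difference is nil.

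**Step 1: the mechanism by hand (3.2.5 rule).** Let m be the post-progression median. The chance of dying before the next scan is d = 1 − 2^(−2/m). Suppose 30% are never confirmable and the rest are confirmed at the first scan if alive. Then:

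- uuPD share = 0.30 + 0.70d
- mean survival overall μ = m/ln 2
- mean survival in cPD = 2 + μ
- mean survival of those dying before the scan = μ − 2(1 − d)/d

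For m = 5.5: d = 0.223 and μ = 7.93. Early deaths are 0.70 × 0.223 = 0.156, so uuPD = 0.456 and 34% of it is early deaths. Mean survival after the first call is 2 + 7.93 = 9.93 months in cPD. In uuPD it is (0.30 × 7.93 + 0.156 × 0.96)/0.456 = 5.5 months.

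For m = 12.6: d = 0.104 and μ = 18.18. uuPD = 0.30 + 0.073 = 0.373, of which 20% is early deaths. The means are 20.2 months in cPD and 14.8 in uuPD.

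These gaps arise although every patient has the same prognosis.

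**Step 2: false-positive rate, 3.2.5 rule, OS from randomization.**

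| Never confirmable | Confirmed at first 2-month scan | Half confirmed per scan |
|---|---|---|
| 30% | 54–77% (m 5.5–12.6); 36–39% (PFS 11, m 14.3) | 74–96% |
| 10% | 77–98% | 98–100% |

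If every surviving patient would eventually be confirmed, the rate is 96–100%. The lowest case tried (50% never confirmable, the rest confirmed at 4 weeks) gives 11–15%. uuPD is the worse group in all or nearly all significant results.

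**Step 3: time origin.** Starting at the first progression call removes the shared pre-progression time that dilutes the bias. For 10% or 30% never confirmable with a first scan at 2 months, the rate becomes 70–100%. A separate set with 250 patients and 10–50% never confirmable gave 17–95% from randomization and 32–100% from first progression.

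**Step 4: if death confirms.** uuPD has 0 deaths by definition, so the estimated hazard ratio is 0.

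- With 1% monthly loss: significant in 90–100% of trials (30% never confirmable) or 53–99% (10%).
- With no loss, 5 to 13 years of follow-up and 30% never confirmable: uuPD averages 0.1 to 3.5 patients, 3–91% of trials have nothing to test, and 9–88% are significant.

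**Step 5: the alternatives.** Under the same null, with death not counted as confirmation, cPD as a time-dependent state from the first progression call rejects in 4–7% of trials. A 4-month landmark rejects in 4.5–7%.

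**The case against.** The case on the other side is substantial.

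- **Standing.** The analysis is one exploratory sentence with no alpha, test or decision rule. The role of helping to interpret OS, cPFS and PFS is given to the Kaplan-Meier plot by arm, not to this comparison. This stands.
- **Size.** A reader might infer that the result would be significant almost always. The documents do not support that. Where the SAP defines OS for the randomized groups (3.1.1), it runs from randomization, which dilutes the bias. Only the size criterion carries a 4-week wait; a new lesion, a T2/FLAIR increase, medical review or an unscheduled MRI could confirm sooner. If 30% of events were confirmed at once (assumed), the rate from randomization is 38–67%. This stands as a limit on magnitude, but those rates are still far above 5%.
- **Conflicting definitions.** A reader might also infer that 8.4.5 itself yields opposite answers. It points to 3.2.5 alone. The death item can be read as endpoint-event wording, since SAP 3.1.3 lists cPD and death separately. That makes 3.2.5 the likelier rule here. Even so, 1.2.3 and 15.3 place death inside the list defining cPD for the same endpoint, so the ambiguity needs settling.
- **Mere missing detail.** The text does not exclude a time-dependent analysis. But the uuPD label is a final status assigned after all follow-up, so the plain reading is two fixed groups, and following it produces the bias.

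**Conclusion.** The concern holds in a limited form. The uuPD-versus-cPD survival comparison is biased whichever rule on death applies, because survival after the first progression call helps decide the group.

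Under 3.2.5 the bias runs against uuPD, with a false-positive rate of roughly 15% to 100% at a nominal 5%; the most favourable case tried gave 11–15%. If death confirms, the hazard ratio is 0 in favour of uuPD or the comparison cannot be made. The direction follows from the definitions. The size rests on assumptions the documents do not settle: time origin, share never confirmable, speed of confirmation, loss, length of follow-up, exponential survival and a log-rank test.

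It would be wrong to read this as a threat to the trial's main claims: no primary or secondary conclusion depends on it. The risk is a misleading exploratory statement about whether unconfirmed progression behaves like pseudo-progression.

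**What to change.** 1. Reconcile SAP 1.2.3 and protocol 15.3 with SAP 3.2.5 on whether death turns an initial progression into cPD. For the 8.4.5 comparison, state that it does not.
2. In 8.4.5, start the clock at the first progression call and name the method. Either fit a Cox model with cPD as a time-dependent covariate, or classify patients by confirmation status at a fixed landmark (for example 4 months, two scan intervals) and compare survival from there among those still alive and under follow-up.

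The cost is SAP wording and minor programming. The landmark drops patients who die or are censored before it: by death alone, 1 − 2^(−4/m), or 40% at a 5.5-month median and 20% at 12.6 months. It also changes the question from ultimately unconfirmed to not confirmed by the landmark. The time-dependent model keeps all patients, so it is the better main version.

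Neither option repairs missing scans. Under protocol 8.4, patients who decline crossover have an end-of-treatment visit and then survival follow-up, so some may stay unconfirmed for lack of imaging. Report the number of scans after the first progression call by group.

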## **Section 9:** Safety

#### 9.1 Adverse events

An overall summary will present the number and percentage of subjects by treatment group with:

- Any TEAE
- Any serious TEAE
- Any TEAE considered as related to study drug, evaluated by the investigator as Definitely Related, Possibly Related or Probably Related or not reported
- Any TEAE considered as related to leukapheresis, evaluated by the investigator as Definitely related, Possibly Related or Probably Related or not reported
- Maximum CTCAE of grades 1 to 5; i.e. a subject with TEAEs at different CTCAE grades will be summarized at the most severe grade
- Any TEAE leading to study drug discontinuation
- Any TEAE leading to death

The summary will also include the total number of TEAEs reported in each treatment group.

The number and percentage of subjects with TEAEs will be presented by SOC, PT and treatment group. Subjects with multiple TEAEs within a SOC or SOC/PT combination will be counted only once for that SOC or SOC/PT combination. Similar summaries will be presented for related TEAEs, serious TEAEs, related serious TEAEs, and TEAEs leading to discontinuation of study drug. TEAEs with CTC Grade 3 or above, and related TEAEs with CTC Grade 3 or above, will be summarized.

Summaries of TEAEs by maximum CTCAE grade will also be presented.

All TEAEs will be listed by subject and start date.

Injection site TEAEs will be listed separately.

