#### Safety population

All subjects in all three cohorts who received at least one immunization with DCVax®-L or placebo. Subjects will be analyzed for safety endpoints according to the treatment they actually received. Subjects will be analyzed in aggregate as well as separately by cohort. Subjects will be analyzed for efficacy endpoints according to their randomized allocation.

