#### Note:

- 1. The conditional survival endpoint is calculated in patients reaching the chosen threshold.
- 2. Subgroup analyses will also be conducted.
- 3. The efficacy analysis for the Informational cohort will not be comparative, as there is only one arm, and will only include descriptive statistics.

Safety data will be reported for the Safety population.

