Visit 4 (Leukapheresis): Patients proceed to leukapheresis as soon as they are sufficiently recovered from surgery, the second Informed Consent Form is signed and after continued eligibility has been determined (unilateral GBM and resection beyond biopsy confirmed, GBM diagnosis confirmed, sufficient tumor lysate generated, negative viral status, adequate bone marrow and liver function, steroid taper). It is recommended but not required that patients complete leukapheresis prior to starting chemotherapy and radiation. An absolute minimum of 45 days is required from the date of leukapheresis to the Baseline Visit.

Visit 5 (Baseline): Visit 5 takes place 2 weeks (± 2 days) after the last day of radiation therapy with concurrent temozolomide chemotherapy. A minimum of 5 immunizations must be available for treatment as determined by the contracted manufacturer. At the Baseline Visit, the patient undergoes AE assessment, an MRI to assess disease progression and blood draws to assess eligibility.

Patients who have evidence of disease progression (measured by MRI, compared with post-surgery MRI and verified by independent review), are not eligible for this study. Patients who do not have progressive disease at baseline are enrolled in the study, and will be randomized to receive DCVax-L or placebo at a 2:1 ratio. All remaining inclusion and exclusion criteria must be met for all patients to be enrolled.

The following tests and examinations are to be performed at Baseline (Visit 5):

- MRI with and without contrast of the brain to confirm absence of disease progression (verified by independent radiology review)
- Physical Examination
- Neurological Exam
- Vitals

- KPS
- CBC and differential, Blood chemistry
- Pregnancy test: Serum hCG pregnancy test is performed on female subjects of child bearing potential
- Anti-DNA antibodies as a marker of autoimmune disease. Results from this test are not required prior to immunizations
- AE assessment

Eligibility to be enrolled in the study will be determined on the basis of the outcome of these tests, which are to be evaluated within the shortest possible time after the Baseline Visit (target <1 week for confirmation of eligibility) to ensure earliest administration of DCVax-L.

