## 13.4. RECORDING AND FOLLOW-UP OF ADVERSE AND SERIOUS ADVERSE EVENTS

All AEs that occur (or that worsen from pre-leukapheresis status) from pre-leukapheresis through 30 days after the patient exits from participation in the trial or last study treatment, (whichever comes later), will be recorded. Adverse events that occur after enrollment but before the first immunization will be considered not related to study drug. Duration, severity, and outcome for each AE will be recorded on the CRF/eCRF Adverse Event Form, and treatment administered for the event will be recorded on the Concomitant Medications pages; this information must also be recorded in the source documentation. Adverse events will be followed until resolution, until no further improvement is expected, or until the patient is lost to follow-up, whichever comes first.

- SAE will be recorded on the Serious Adverse Event Form, which will be faxed or e-mailed to the Sponsor, or its designee, indicated in the study manual within 24 hours of becoming aware of the event. A corresponding AE must be recorded in the source documents and the eCRF.
- All SAE must be followed until the event has resolved, until no further improvement is expected, or until the patient has been lost to follow-up, whichever comes first.
- AE beginning more than 30 days after the last treatment, that the Investigator considers related to study treatment, will be reported to the Sponsor or its designee, indicated in the study manual at any time such events occur.
- Toxicities that were present at the study start and that worsen during the study should be reported as beginning on the date the event worsened, not the date it began pre-study. Event text may include the word "worsened" or "exacerbated."

 All AEs are documented in the source document and on the AE Form (located in the CRF/eCRF). The intensity of all AEs not localized to the injection site of the study drug is graded according to the U.S. National Cancer Institute (NCI) Common Terminology Criteria for Adverse Events (CTC) version 3.0 (Appendix H).

http://ctep.cancer.gov/protocoldevelopment/electronic applications/docs/ctcaev3.pdf

 Grade refers to the severity of the AE. The CTCAE v3.0 displays Grades 1 through 5 with unique clinical descriptions of severity for each AE based on this general guideline:

Grade 1 Mild AE

Grade 2 Moderate AE

Grade 3 Severe AE

Grade 4 Life-threatening or disabling AE

Grade 5 Death related to AE

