## 14. POSSIBLE RISKS AND SIDE EFFECTS; SPECIAL MONITORING DURING INVESTIGATIONAL STUDIES

Some patients may expect to have local injection site reactions. Local reactions consist primarily of mild to moderate pain at the injection site, rash, pruritus, induration, tenderness, vesiculation, abscess formation, ulceration or necrosis at the site of injection, and/or regional lymphadenopathy.

Serious systemic reactions to attributed to DCVax-L have not been observed to date. Mild fever or fatigue has been observed in patients injected with DCVax-L. Systemic reactions may include the following symptoms: sneezing, coughing itching, shortness of breath, abdominal cramps, vomiting, diarrhea, tachycardia, hypotension and respiratory failure in severe cases. Systemic allergic reactions including anaphylaxis must be immediately treated with Epinephrine HCL 1:1000.

The risks to newly diagnosed GBM patients as a result of intradermal (i.d.) administration of DCVax-L in the clinical trial may include the following:

- Fatigue, fever, nausea, vomiting, and citrate toxicity secondary to leukapheresis. Leukapheresis. Leukapheresis procedures for blood collection are well established and controlled.
- Fatigue, fever, nausea and vomiting secondary to treatment of the DC with Leukine® or IL-4. After the culture period the DC are washed vigorously to remove residual Leukine® and IL-4, thus minimizing adverse toxicity.

- Administration of DCVax-L may result in local reactions at site of injection resulting in discomfort, bruising, and/or skin ulceration.
- Administration of DC loaded with cell lysate, such as tumor cell lysate, could theoretically cause autoimmunity due to the presence of self-antigens. However, no signs of autoimmunity were observed in the clinical trials with DCVax-L or other related products in altogether more than 1100 patients (see also sections 2.2 and 4).

Furthermore, patients with GBM, irrespective of their immunization status with DCVax-L, are expected to experience symptoms arising from progression of their disease, which may include any or all of the following: headaches, seizures, motor dysfunctions, speech problems, sensory disturbances, altered consciousness, and other sequelae of brain cancer.

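### SAP 9.1 summarises leukapheresis harm only as treatment-emergent events, by treatment group, in immunised subjects, so patients who had leukapheresis but no dose are left out

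*Combined protocol and SAP*

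**What the plan says.** SAP 9.1 introduces the adverse-event table with "An overall summary will present the number and percentage of subjects by treatment group with", and one item in the list that follows is "Any TEAE considered as related to leukapheresis, evaluated by the investigator as Definitely related, Possibly Related or Probably Related or not reported". The note under SAP 2.3 adds "Safety data will be reported for the Safety population". SAP 2.2 defines that set as "All subjects in all three cohorts who received at least one immunization with DCVax®-L or placebo", and also says "Subjects will be analyzed in aggregate as well as separately by cohort". The abbreviation list spells out TEAE, but neither the SAP nor the protocol gives an onset rule or reference date for it. SAP Section 5 counts subjects screened, randomised and entered into each cohort, but not subjects who had leukapheresis.

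The timing is in protocol v7.0. Section 8.2 states "An absolute minimum of 45 days is required from the date of leukapheresis to the Baseline Visit". Section 8.1 allows a repeat harvest only if product can be made and released before Baseline, which it puts at roughly 44 days. Randomisation follows within a week of Baseline, and the first injection comes about a week after Baseline (section 8.1; Appendix A footnotes).

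Section 14 lists "Fatigue, fever, nausea, vomiting, and citrate toxicity secondary to leukapheresis" among the risks. Sections 13.2 to 13.4 record adverse events from the pre-leukapheresis visit, once the second consent is signed. Appendix A schedules AE assessment at Visits 3 and 4. Section 13.5 adds a telephone report for serious events suspected to be related to the procedure.

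**The concern.** Neither the vaccine nor the placebo can be made without leukapheresis, so its harm is part of the burden of the treatment. The natural denominator is everyone who had the procedure, and the natural window opens on the day it was done. The planned row uses neither. It takes its population and its event type from the drug tables, where the exposure of interest is the injection. It also splits by arm a procedure that is finished before any arm is assigned.

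What is at stake is whether the report can state a leukapheresis event rate at all. The protocol names the risks and records the events, but no planned table gives a rate in the people exposed.

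**Working it through.** There is no planned leukapheresis figure to reproduce. The check is date arithmetic and a comparison of definitions.

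**1. Timing.** Inputs: at least 45 days from leukapheresis to Baseline (protocol 8.2); about 44 days for a repeat (8.1); about 7 days from Baseline to first injection (Appendix A footnotes).
- Single harvest: 45 + 7 = about 52 days, or 7.4 weeks.
- Repeat harvest: 44 + 7 = about 51 days, or 7.3 weeks.
- Recommended order, with leukapheresis before chemoradiation: 42 days of treatment (Appendix C) + 21 days from last radiation to Day 0 (Appendix B) = about 63 days, or 9 weeks.

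The procedure also precedes randomisation. Among randomised patients, an arm difference in events that began before allocation can therefore reflect only chance, or who went on to be dosed.

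**2. Population.** The Safety population requires one immunisation. Three groups can have leukapheresis and fall outside it:
- patients for whom too few doses were made, who cannot continue (8.1);
- patients with progression at Baseline who did not enter a treated cohort (7.2, 8.2);
- randomised patients who were never injected.

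This exclusion does not depend on how TEAE is defined. Because Section 5 gives no leukapheresis count, the planned output does not supply the right denominator either.

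**3. Event type.** Two readings of TEAE are open.
- *Onset after first dose.* The nearest date rule in the SAP is in 6.3, which separates prior from concomitant medication at first study drug on Day 0. On this reading, acute events fall about 7 weeks or more too early to be counted.
- *Onset from leukapheresis.* Protocol 13.4 records worsening relative to pre-leukapheresis status. On this reading, acute events in dosed patients are counted, but the drug TEAE tables then take in the chemoradiation period (42 to 49 days, Appendix C).

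**4. Missing causality.** The row counts an unreported relationship as related. On the first reading, an event months after dosing with no leukapheresis rating would enter the row while a genuine acute event would not.

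**5. How much turns on the definition.** Illustration only: expected count = N × p × f. N = 331 is the ITT size, a stand-in because the Safety population size is not given. p is the assumed share of patients with a leukapheresis-related event, and f is the assumed share of those events that qualify as TEAEs. The effect in step 4 is not included.

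| Assumed p | First reading (f = 0 to 5%) | Second reading (f = 100%) |
|---|---|---|
| 5% | 0 to 0.8 | 16.6 |
| 10% | 0 to 1.7 | 33.1 |
| 20% | 0 to 3.3 | 66.2 |

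For example, 331 × 0.20 × 0.05 = 3.3 and 331 × 0.20 × 1 = 66.2. The values of p and f are not from the documents. The table shows only that the same data give very different rows under a rule the SAP leaves unstated.

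**The case against.** The strongest reply is that the documents leave room for a more favourable reading.

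- **TEAE is undefined.** A reader might infer that the row is bound to be close to zero. The documents do not support that. AE collection starts before leukapheresis, which fits a wider definition, and counting unreported causality as related could push the row up even under the narrow one. This part of the reply stands.
- **Aggregate analysis is planned.** SAP 2.2 provides pooled as well as by-cohort results, so the arm split is not the only view. This stands, but the pooled set still contains only immunised subjects.
- **Other cohorts were treated.** Under protocol v4.0, patients progressing at Baseline could receive the vaccine in the informational arm, and SAP 1.6.2 describes a randomised pseudo-progression cohort. Those who were immunised are in the Safety population. The summary of changes shows informational enrolment ending with v5.2 and the pseudo-progression arm removed in v6.0, so this rescues some patients and not others.
- **All data will be listed (SAP 4.1).** Pre-dose events may appear in listings. But listings are by treatment group, which never-allocated patients lack, 9.1 names only TEAE listings, and a listing is not a rate.
- **Section 13.4.** A reader might cite "Adverse events that occur after enrollment but before the first immunization will be considered not related to study drug" as conflicting with a TEAE window that includes chemoradiation. It does not. Enrolment coincides with randomisation and follows the end of chemoradiation, so the sentence covers roughly a week.

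The protocol also calls leukapheresis well established and controlled. That bears on how much harm to expect, not on the choice of denominator.

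**Conclusion.** The point holds in a limited form. Under any definition of TEAE, the planned summary omits patients who had leukapheresis and were never immunised, and its arm split is uninformative for a procedure completed before randomisation. If TEAE means onset after the first dose, the summary also misses acute events in dosed patients and may count later events whose causality was not reported. That second part is conditional on a rule the SAP does not state.

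The number omitted cannot be given. A reader might scale up from the 331 randomised by assuming some share was never dosed. The documents give no count of leukapheresis procedures, and 331 is neither the number dosed nor the Safety population, so such a figure would have no basis.

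The efficacy analyses are untouched. The vaccine-versus-placebo safety comparison is affected only through the TEAE definition. This is a worthwhile correction at low cost.

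**What to change.** In SAP 9.1, replace the leukapheresis row with one pooled table, without an arm split:
- **Subjects:** everyone with at least one leukapheresis, with that number reported in the table and added to Section 5.
- **Events:** all AEs and SAEs rated related to leukapheresis, with onset at any time from the leukapheresis date, shown separately for before and after first immunisation.
- **Causality:** events with a missing leukapheresis rating on their own line, not merged with those rated related.

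State in 9.1 that a TEAE is an event with onset or worsening on or after the first immunisation, so that the drug tables exclude toxicity arising during chemoradiation.

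The cost is SAP wording and one table. Protocol 13.2 to 13.4 already require these events to be recorded from the second consent. Protocol 18.5 words the case-report-form requirement for enrolled patients, so the sponsor should confirm before lock that records for patients who had leukapheresis but were not enrolled are in the database. The reported leukapheresis event rate may look less favourable.
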